### **7.6.8 *Other Safety Considerations***

#### **7.6.8.1 *ECG***

Summary statistics (n, mean, standard deviation, median, minimum, and maximum) will be presented for each ECG parameters and the corresponding changes from baseline by treatment and visit. The baseline value is defined as the last measurement before the first dose. ECG readings will be evaluated by the Investigator and abnormalities, if present, will be listed.

The frequency distribution of subjects' maximum recorded post-dose QTcF, PR, QRS and  $\Delta$ QTcF will be tabulated by treatment and summarized within the CSR text for the following ranges:

For QTcF:  $QTcF \leq 450$  msec,  $450$  msec  $< QTcF \leq 480$  msec,  $480$  msec  $< QTcF \leq 500$  msec,  $QTcF > 500$  msec

For PR:  $PR \leq 200$  msec,  $PR > 200$  msec

For QRS:  $QRS \leq 120$  msec,  $QRS > 120$  msec

For  $\Delta$ QTcF:  $\Delta QTcF \leq 30$  msec,  $30$  msec  $< \Delta QTcF \leq 60$  msec,  $\Delta QTcF > 60$  msec

Individual QTcF, PR, QRS or  $\Delta$ QTcF values meeting these criteria will be flagged in the data listing.

#### **7.6.8.2 *Vital Sign***

Vital signs parameters (systolic blood pressure, diastolic blood pressure, heart rate, respiratory rate and body temperature) will be listed. Summaries of vital sign parameters will be provided for each vital sign parameter at corresponding visits by treatment and respective changes from baseline. Subjects with vital signs outside of a pre-specified range will also be listed.

The following criteria will be used to determine vital sign results that are outside of a pre-specified range, where changes from baseline are based on matched postural positions and are calculated as parameter value - baseline parameter value:

**Table 7.6.8.2-1: Vital signs criteria**

Vital sign	Criteria
Heart Rate(bpm)	Value > 100 and change from baseline > 30, or Value < 55 and change from baseline < -15
Systolic BP(mmHg)	Value > 140 and change from baseline > 20, or Value < 90 and change from baseline < -20
Diastolic BP(mmHg)	Value > 90 and change from baseline > 10, or Value < 55 and change from baseline < -10
Respiration(breaths/min)	Value > 16 or change from baseline > 10
Temperature (°C)	Value > 38.3°C or change from baseline > 1.6°C

**7.6.8.3 Conventions of ECG Data**

All available non-missing values of ECG parameters should be used in the listings, summarizations, and analyses. However, if QTcF is missing and RR in seconds is available, then QTcF will be calculated as

$$QTcF = \frac{QT}{RR^{1/3}}$$

If both QTcF and RR in seconds are missing, then QTcF will be calculated as

$$QTcF = \frac{QT}{(60/HEART\ RATE)^{1/3}}$$

**7.6.8.4 Physical Examination Findings**

All physical examination abnormal findings will be listed per subject by visit.

**7.7 Pharmacokinetic Analysis**

Summary statistics of Ctrough (mean, SD, geometric mean, % CV, median, min, and max) for the PK analysis population will be provided by treatment and study day.

Similar statistics will be provided for post-dose concentration on Day 46 and Day 48.

The listing of Concentration of BMS-931699 by treatment and study day will also be provided.

[REDACTED]

[REDACTED]

[REDACTED]

[REDACTED]

[REDACTED]

## **7.9 Immunogenicity Analysis**

Serum for anti-BMS-931699 antibody titers will be drawn at Day 1, and during the ST period. Subjects who discontinue study medication will have a serum samples collected at the early termination visit and 42 days after the last dose of study medication (42 days follow up). Lack of immunogenicity is defined as the absence of a positive response.

For all summaries and listings unless specified otherwise, an anti-drug antibody (ADA) positive relative to baseline immunogenicity response is defined as:

- 1) a missing baseline immunogenicity measurement and a positive laboratory reported immunogenicity response post-baseline
- 2) a negative laboratory reported baseline immunogenicity response and a positive laboratory reported immunogenicity response post-baseline
- 3) A positive laboratory reported baseline immunogenicity response and a positive laboratory reported immunogenicity response post-baseline that has a titer value of 4 fold or greater than the baseline titer value.

All other immunogenicity measurements will be classified as negative immunogenicity response.

In addition, persistent anti-drug antibody is defined as anti-drug antibody positive occurrence relative baseline detected at 2 or more consecutive time points at least 3 months apart. Immunogenicity Frequencies

### **7.9.1 Immunogenicity Frequency**

The number (and percentage) of anti-drug antibody positive subjects relative to baseline will be provided. Similar analyses will be performed for persistent anti-drug antibody positive subjects (relative to baseline).

The number (and percentage) of subjects whose last sample is the only anti-drug antibody positive sample relative to baseline will be presented also.

A listing of titer values for all ADA positive subjects (laboratory reported) will be provided for antibodies against the domain antibody portion of the drug.

## 7.10 Interim Analyses

### 7.10.1 *Interim Safety/RO Analysis at Day 29*

When at least 6 patients per treatment arm have either reached Study Day 29 or discontinued, an interim analysis (IA) for safety and RO will be performed. The safety analysis will focus on incidence and severity of all adverse events (AEs), serious AEs and pre-established Events of Special Interest such as infection AEs and any other safety analysis requested by DMC. A separate document, DMC charter, describes the scope of these analyses. For RO: the median RO at Day 29 for each treatment arm will be calculated. Based on the results of this interim analysis, a decision will be taken regarding the doses that will be carried forward into Part 2 of the study. Specifically, dosing regimens originally included in Part 1 may be discontinued and/or new dosing regimens may be added according to the following criteria:

Safety:

The DMC in conjunction with an unblinded internal monitoring team (The details of the members are provided in [Section 2.3.2](#)) may require one or more doses to be discontinued if stopping criteria are met or other safety signals arise that the Medical Monitor and/or DMC consider of sufficient concern.

Receptor Occupancy:

- If median RO of any dose is <20%, the sponsor may consider dropping that dose
- If the median RO for all doses is >90% the sponsor may consider adding or replacing a dose in Part 2 of the study to ensure an adequate pharmacodynamic range (dose not to exceed 12.5 mg weekly)

Dose decrease and/or reduction of frequency of administration may also be considered if RO results fall outside the parameters indicated above. This adjustment may occur for safety reasons or in case unforeseen RO profiles observed in SLE patients. The decision to adjust dose and/or frequency will be taken after review of the data by the clinical team. Any decision related to safety reasons will be taken in conjunction with DMC recommendations.

RO analysis in interim analyses 1 will be done by a Pharmacokinetic scientist or a Pharmacometrics analyst. If dose/doses are adjusted based on this RO analysis, then the interim analyses results may be included in CSR as an appendix.

### **7.10.2    *Interim Analysis for Futility and Dose Adaptation at Day 85***

After 30 subjects per treatment arm (including the subjects from Part 1) have completed at least 84 days of the treatment period or discontinued the treatment, an interim analysis will be conducted to assess the futility of the BMS-931699 dose arms and the overall safety. The results of the interim analysis will be reviewed by an unblinded sponsor team (Independent of the study team) who will provide recommendations to the blinded study team. The details of the members are provided in [Section 2.3.2](#). The blinded study team will make the decision. The unblinded BMS team may recommend to:

- maintain the current design;
- drop a certain dose arm(s) and equally randomize the remaining unallocated subjects to the remaining arms;
- stop the study if all dose arms need to be dropped for safety or futility reasons.

Any decision related to safety reasons will be taken in conjunction with DMC recommendations.

The interim analysis for futility and dose adaption will be performed on the BICLA response at Day 85 of those 30 subjects per arm and BICLA response at Day 169 of those subjects who have completed 168 days of treatment or discontinued the treatment using a Bayesian predictive approach. This analysis assumes that the BICLA at Day 85 and at Day 169 in the subjects who have not yet been observed will be similar to what were observed for the subjects included at the interim analysis at Day 85 and Day 169, respectively. As such the unobserved data will be simulated from the predictive distribution conditional on the interim data and the prior distribution of the treatment difference (using a non-informative prior). Under the Bayesian framework, the posterior distribution of the treatment difference (BMS-931699 active dose – Placebo) will be constructed to determine the predictive probability of a successful outcome (i.e., reach statistical significance) at the planned end of the trial for each dose arm. Based on computer simulations of the operating characteristics of the study design, the futility threshold in this interim analysis is set to 0.2. For the comparison of interest, if the predictive probability of a successful outcome at the planned end of the trial falls below 0.2, that BMS-931699 dose arm is deemed futile in terms of BICLA response. However, the final futility will also incorporate the results from the efficacy endpoints such as but not limited to SRI(4), ACR28 and some biomarkers such as but not limited to C3, C4, ANA and anti-dsDNA. The final decisions will be made based on the discussions using the pre-specified rules in the *Interim Analysis SAP* and/or the evidence from the totality of the data.

The proposed stopping rules at the interim analysis, based on the futility assessment and the overall safety assessment, are as follows:

- Rule 1: Drop the futile dose arm(s) and the dose arm cannot be dropped until the lower dose arm has been dropped.
- Rule 2: Drop the dose arm(s) with safety issues identified;

- Rule 3: If safety issues are identified in all dose arms or all dose arms are futile, stop the study.

In case dosing arms are dropped following the interim analysis, the remaining unallocated subjects will be randomized into the remaining arms.

If the predictive probability of success for each active arm versus placebo is greater than or equal to 0.9, then the BMS team may also recommend adding an additional dose arm at lower dose level than current active doses to explore the suboptimal dose.

In that case, the remaining un-allocated subjects with up to 40 additional subjects will be randomized into the remaining arms and the new dose arm based on the new randomizations schedule.

A separate document, *Interim Analysis SAP*, has been developed in order to provide a set of rules with clarifying details as a guidance to make any decisions about the dose adaptation.

[REDACTED]

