After 30 subjects per treatment arm (including the subjects from Part 1) have completed at least 84 days of the treatment period or discontinued the treatment, an interim analysis will be conducted to assess the futility of the BMS-931699 dose arms and the overall safety. The results of the interim analysis will be reviewed by an unblinded sponsor team who will provide recommendations to the blinded study team. The blinded study team will make the decision. The unblinded BMS team may recommend to:

- Maintain the current design;
- Drop a certain dose arm(s) and equally randomize the remaining unallocated subjects to the remaining arms;
- Stop the study if all dose arms need to be dropped for safety or futility reasons.

The interim analysis for futility and dose adaption will be performed on the BICLA response at Day 85 and Day 169, of those 30 subjects per arm who have completed 85 days of treatment or discontinued the treatment, using

a Bayesian predictive approach.² This analysis assumes that the BICLA response at Day 85 and at Day 169 in the subjects who have not yet been observed will be similar to those observed for the subjects included in the interim analysis at Day 85 and Day 169, respectively. As such, the unobserved data will be simulated from the predictive distribution conditional on the interim data and the prior distribution of the treatment difference (using a non-informative prior). Under the Bayesian framework, the posterior distribution of the treatment difference (BMS-931699 active dose – Placebo) will be constructed to determine the predictive probability of a successful outcome (ie, reach statistical significance) at Day 169. Based on computer simulations of the operating characteristics of the study design, the futility threshold in this interim analysis is set to 0.2. For the comparison of interest, if the predictive probability of a successful outcome at the planned end of the trial falls below 0.2, that BMS-931699 dose arm is deemed futile in terms of BICLA response. However, the final futility will also incorporate the results from SRI(4), ACR28 and some biomarkers (C3, C4, ANA and anti-dsDNA).

The proposed stopping rules at the interim analysis, based on the futility assessment and the overall safety assessment, are as follows:

- Rule 1: Drop the futile dose arm(s) and the dose arm cannot be dropped until the lower dose arm has been dropped.
- Rule 2: Drop the dose arm(s) with safety issues identified;

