8 STATISTICAL CONSIDERATIONS

8.1 Sample Size Determination

The sample size calculation is based on power to compare the proportion of subjects who achieve BICLA response (the BICLA response rate) at Day 169 between BMS-931699 dose arm and placebo arm. With a one-sided continuity corrected chi-squared test at significance level 0.05, data from 70 randomized and treated subjects per arm will provide at least 89% power to detect a 25% increase in the BICLA response rate in the active treatment arm(s) [(ie, 50% response rate in BMS active arm(s)] compared to placebo, and provide 74% power to detect a 20% increase in the BICLA response rate in the active treatment arm(s) [(ie, 45% response rate in BMS active arm)] compared to placebo, assuming that the placebo arm has 25% response rate which is reasonable based on the EMBLEM phase 2 trial results²¹. No adjustment will be made for multiplicity. Subjects who discontinue treatment/study prior to Day 169 will contribute to the data that will be analyzed for BICLA response at Day 169 (discontinuation will indicate no BICLA response). Therefore, no adjustment will be made for discontinuations.

The primary efficacy analysis will be conducted on all randomized patients who received at least one dose of the study drug. In order to get 70 randomized and treated subjects per arm, an adequate number of subjects will need to meet the inclusion/exclusion criteria at screening.

If the interim analysis for futility and dose adaptation suggests that an additional dose arm (at a lower dose level) needs to be added, then up to 40 additional subjects may be randomized.

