#### **7.5.4      *Sensitivity Analyses***

Sensitivity analysis for the primary endpoint: Adjustment for the randomization strata using Cochran-Mantel-Haenszel (CMH) methods will be applied on the primary endpoint.

If at least 15-20% of total subjects through all treatment arms in the efficacy analysis population discontinued due to any reasons other than Lack of Efficacy (LOE), AE or Unknown reason, a sensitivity analysis may be performed. The subjects who have missing response due to premature discontinuation with reasons other than LOE, AE or Unknown will be excluded from the analyses, hence defining the sensitivity analysis population. The sensitivity analysis will be carried out for the primary and selected secondary endpoints (SRI (X): X = 4, 6.) based on the sensitivity analysis population.

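### The interim Day 169 response rate counts dropouts as failures at once but continuing subjects only after 168 days, so it is understated in every arm with dropout

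*SAP*

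**What the plan says.** - **Trigger** (SAP 7.10.2): "After 30 subjects per treatment arm (including the subjects from Part 1) have completed at least 84 days of the treatment period or discontinued".
- **Day 169 data** (SAP 7.10.2, and the same words in protocol 8.6.2): "BICLA response at Day 169 of those subjects who have completed 168 days of treatment or discontinued the treatment". Nothing requires a discontinued subject's Day 169 date to have passed.
- **Outcome of a discontinued subject**: protocol 8.1 states "discontinuation will indicate no BICLA response". SAP 8.1.1 scores such subjects as non-responders at all later efficacy visits.
- **Extrapolation** (SAP 7.10.2): "This analysis assumes that the BICLA at Day 85 and at Day 169 in the subjects who have not yet been observed will be similar". The reference for that similarity is the interim data set.
- **Use**: the predictive probability (PP) of final significance is compared with 0.2 for futility, and with 0.9 in every active arm for adding a lower dose. On the first threshold: "Based on computer simulations of the operating characteristics of the study design, the futility threshold in this interim analysis is set to 0.2".
- **Brakes on the decision**: Rule 1 ("the dose arm cannot be dropped until the lower dose arm has been dropped"), plus SRI(4), ACR28, biomarkers and the totality of the data. SAP 7.10.2 refers to a separate Interim Analysis SAP for details.
- **A different set in the protocol synopsis**: it takes both time points from one group, "Day 85 and Day 169, of those 30 subjects per arm who have completed 85 days of treatment or discontinued the treatment".

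**The concern.** Take two subjects randomised on the same day, 13 weeks before the data cut. One has stopped treatment and is already in the Day 169 set as a failure. The other is still on treatment, could still respond, and does not enter for another 11 weeks. The interim is triggered at 84 days, so many continuing subjects are in the second position. The set therefore holds too many failures, and the similarity assumption carries that excess into the prediction for everyone not yet observed.

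Dropout already counts against an arm in the endpoint itself. This is a further penalty that comes only from the timing of inclusion. Two doses with the same true Day 169 rate could get different futility probabilities because their dropout differs, at the analysis that decides which doses continue. The 84-days-or-discontinued trigger has the same flaw to a smaller degree. The synopsis wording keeps the discontinued subjects and does not avoid it.

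**Working it through.** **1. The plan's own figure.** SAP section 5: 70 per arm, one-sided 0.05, continuity-corrected chi-square, placebo 25%. The effective size after the correction is n' = (n - 1/d)²/n, and z = [d√n' - 1.645√(2p̄(1-p̄))] / √(p₁q₁ + p₂q₂).
- 50% vs 25%: n' = 66²/70 = 62.2, z = 1.279, power 0.90 (exact 0.898). The plan says at least 89%.
- 45% vs 25%: n' = 65²/70 = 60.4, z = 0.674, power 0.75 (exact 0.747). The plan says 74%.

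The stated power reproduces, so the same final test is used below.

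**2. Direction of the bias.** Subjects whose Day 169 date has passed (due), whether they completed or discontinued, respond at the true rate p. Early discontinuers who are not yet due add to the denominator only. Hence

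expected rate ≈ p × due / (due + early discontinuers),

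which is below p whenever there is dropout among subjects not yet due.

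**3. Assumed inputs (not in the documents).** Accrual of 1, 1.5 or 2 subjects per week per arm. Constant-hazard dropout of 20% by Day 169 (range 15-25%). Part 1 capped at 10 per arm, with Part 2 opening 4 weeks after the sixth subject per arm reaches Day 29. There were 3,000 simulated five-arm interims per scenario (standard error about 0.5 points), with flat priors. Day 169 data only, except in step 7.

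**4. Rates at 20% dropout in all arms.**

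| Accrual/week/arm | Due + early discontinuers | True 50% reads | True 25% reads |
|---|---|---|---|
| 1 | 17.6 + 2.5 | 50 × 17.6/20.1 = 43.8% | 21.9% |
| 1.5 | 11.7 + 3.7 | 50 × 11.7/15.4 = 38.0% | 19.0% |
| 2 | 10.0 + 4.1 | 50 × 10.0/14.1 = 35.5% | 17.7% |

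A separately written simulation gave 44% and 38% for a true 50% at 4 and 6 subjects per arm per 28 days (1 and 1.5 per week). Limited to subjects past 168 days, its set returned 50%.

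**5. Chance that PP < 0.2 (%), 20% dropout.**

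| Accrual | 50% vs 25%: as written / modelled / 168-day cohort | 25% vs 25%: same order |
|---|---|---|
| 1 | 11.5 / 9.5 / 8.9 | 61.8 / 60.8 / 57.9 |
| 1.5 | 15.4 / 11.7 / 11.0 | 57.5 / 53.9 / 52.3 |
| 2 | 17.0 / 12.1 / 8.1 | 55.7 / 51.4 / 43.5 |

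'Modelled' means a by-arm discontinuation hazard times the completer response rate. Over equal dropout of 15-25%, the excess of the written rule over the modelled one is 1.4-2.7, 2.8-4.5 and 3.4-5.8 points. Raising the modelled threshold to 0.21-0.25, to match the plan's flag rate under 25% vs 25%, leaves 1.0-2.9 points. The rest is a threshold shift.

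**6. Unequal dropout, 50% vs 25%, as written / modelled (%).**
- 25% active, 15% placebo: 14.3/9.9, 20.5/11.6, 23.1/12.3.
- 15% active, 25% placebo: 9.3/9.6, 10.0/10.6, 10.9/11.4.
- Four doses all truly 50%, dropout 10/15/25/30% (placebo 20%), at 2 per week: 9.4/11.1/20.5/24.0 as written, against 9.8-12.1 modelled.

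**7. Adding Day 85 data.** The documents do not say how Day 85 is linked to Day 169, so a transition model was assumed: Day 85 rate 0.9 times the Day 169 completer rate, and 75% of Day 85 responders still on treatment responding at Day 169. At 20% dropout, the plan's sets against cohorts defined by time since randomisation give 10.6 vs 8.3, 14.0 vs 9.8 and 15.0 vs 10.0. The excess is 2.3, 4.2 and 5.0 points, against 2.6, 4.4 and 8.9 over the 168-day cohort without Day 85.

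**8. All four active arms with PP < 0.2 when all are truly 50%, as written vs modelled (%).** 20% dropout throughout: 1.1 vs 0.9, 1.8 vs 1.4, 2.0 vs 1.0. With 25% active and 15% placebo: 1.9 vs 1.1, 3.4 vs 1.3, 5.0 vs 1.5.

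**The case against.** The strongest reply is that most of these figures are not for the planned analysis. The plan also uses Day 85 response, the Interim Analysis SAP may define the sets properly, and 0.2 was chosen by simulating the design, possibly with dropout included. All of this could reduce the problem. It does not remove it on the text available: nothing there restricts the set by time since randomisation, and Day 85 data lessen the excess under the assumed link without abolishing it. A threshold calibrated at equal dropout would still leave the between-dose difference in step 6.

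Second, a PP below 0.2 in one arm is not a decision. Rule 1, the other endpoints and the totality of the data intervene. At 20% dropout in all arms, the chance of all four effective arms falling below 0.2 rises by 1 point or less. This stands, and it limits the practical effect.

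Third, the modelled comparator fits the same constant hazard that generated the data, so its gain is a best case. This also stands.

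A reader might also take SAP 7.5.4 as showing that the sponsor expects 15-20% dropout. It does not. "If at least 15-20% of total subjects through all treatment arms in the efficacy analysis population discontinued due to any reasons other than" certain causes is a condition under which a sensitivity analysis may be run, not a forecast, so the dropout range here remains an assumption.

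**Conclusion.** The written rule understates each arm's Day 169 rate whenever there is dropout and accrual is still running. That follows from the definitions alone. The size rests on assumed accrual and dropout: at 20% dropout the loss is about 6 to 14 points on a true 50%, and the excess chance of a false futility flag is 2.0, 3.7 and 4.9 points over the modelled version, partly a threshold shift.

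Three stronger readings are not supported.
- **Arms with most dropout lose most.** This is true relative to the true rate, but not always in points. In one scenario, placebo at 25% with 30% dropout lost about 4.4 points, while an active arm at 50% with 15% dropout lost about 4.9.
- **PP is always too low.** With more dropout on placebo there is no consistent excess of futility flags. That pattern is plausible, because protocol 3.5 requires stopping for new lupus manifestations that need non-protocol treatment.
- **Effective doses will be dropped or the study wrongly stopped.** The brakes in SAP 7.10.2 and step 8 argue against this at equal dropout. It is more of a risk if dropout is higher on active treatment.

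The rule should be corrected. Confidence in its practical size is only moderate, because the Interim Analysis SAP and the simulations behind 0.2 were not available. If they already handle this, only the wording needs to change.

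**What to change.** In protocol 8.6.2, SAP 7.10.2 and the Interim Analysis SAP:

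1. Keep subjects who have already discontinued as known failures in the final-outcome count, but do not predict others from the completed-or-discontinued rate.
2. Predict subjects not yet observed from either (a) a by-arm model of remaining discontinuation risk (events over time at risk) times the response rate among 168-day completers; or (b), more simply, the rate among subjects randomised at least 168 days before the cut, whether they completed or discontinued (84 days for the Day 85 rate).
3. Confirm 0.2 and 0.9 by simulation under the revised rule, under null and alternative and with unequal dropout by arm.
4. Reconcile the synopsis with protocol 8.6.2 and SAP 7.10.2 on which subjects supply Day 169 data.

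All of this should be done before the unblinded team sees interim data.

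**Cost.** Wording in three documents and a rerun of the threshold simulations. At an unchanged 0.2 and equal dropout of 15-25%, ineffective arms (25% vs 25%) are flagged less often, by 1.0-5.5 points with (a) and 3-14 points with (b). For (a), a threshold of about 0.21-0.25 restores the plan's null rate. The figures for (b) use the cohort rate alone, which forgoes about 2-5 Day 169 outcomes per arm. Keeping known failures and giving everyone else an all-subject rate leaves part of the bias: at 25% dropout, false flags are 9.1, 11.9 and 13.2%, against 8.7, 10.5 and 11.7% modelled and 11.4, 15.0 and 17.5% as written. Option (a) is therefore preferable if the team can support it.
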